
2.0 Background/Scientific Rationale

Among females of reproductive age, suicide is the second leading cause of death, accounting for 13% of all female deaths in America¹. Although males are more likely to die by suicide (due to higher-lethality methods), females are three times as likely to experience suicidal ideation (SI) or attempt suicide². This sex difference manifests between puberty³ and menopause⁴, implicating fluctuations in ovarian hormones. Despite this, *no published longitudinal or experimental studies have directly examined ovarian hormone effects on suicide risk*.

In cross-sectional studies, suicide attempts occur most frequently peri-menstrually—that is, in the weeks before and during menses—when the ovarian hormones E2 P4 fall rapidly. The perimenstrual weeks have been repeatedly linked with greater risk of suicidal behaviors in cross-sectional hospital and postmortem studies^{5–8}. While this further implicates hormone changes in proximal suicide risk, *the impact of this work is limited by a lack of longitudinal or experimental data, and a lack of data regarding mechanisms*.

One possible mechanism of perimenstrual suicide risk is rapid perimenstrual withdrawal from E2 and P4 (Fig 2), as well as withdrawal from the antidepressant⁹ and sedative^{10,11} effects of their **GABAergic neuroactive steroid metabolites**. The PI's recent longitudinal and experimental studies (K99-MH109667¹²), which form the premise for the proposed work, provide the first (1) longitudinal evidence that daily SI and behavior peak perimenstrually, and (2) experimental evidence that E2+P4 withdrawal causes increased perimenstrual suicide risk that can be prevented by administering stabilizing doses of E2+P4¹². **The proposed mechanistic trial** responds to the RFA by integrating the PI's experimental paradigm with molecular, genetic, and behavioral measurements to examine the mechanisms by which perimenstrual E2+P4 withdrawal (vs. experimental stabilization) increases proximal suicide risk. We examine mediation across levels of analysis, including changes in neuroactive steroid metabolites (serum neuroactive steroid levels, neuroactive steroid biosynthetic enzyme mRNA expression in peripheral monocytes) as well as hopelessness and hyperarousal.

Defining and Operationalizing Behavioral Constructs

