We will also collect a urine sample and perform rapid urine toxicology screens for amphetamines, barbiturates, benzodiazepines, cocaine, opioids, cannabis, and methamphetamine on-site through the CRC nursing staff using Alere iCup 12-Panel Drug Test with temperature-sensitive strips. Positive tests will be used primarily for data quality assurance and covariate purposes. Individuals with positive test results will be allowed to continue the study provided that the participant demonstrates an ability to safely complete all study procedures. When there is any positive test that is not

accounted for by an existing prescription, the participant's test results will be reviewed with the study physician and PI at routine team meetings.

At all 10 laboratory assessments during active treatment with placebo or E2/P4, participants will provide blood (35ml at each visit) to be assayed for E2/P4, neuroactive steroids, and from which we will perform RNA gene expression assays, to evaluate the success of the hormone in achieving stable luteal phase levels of E2/P4/ALLO, as well as more stable gene expression markers of risk across various systems (neurosteroidogenic enzymes, GABA-A receptor subunits, and other mechanisms such as inflammatory cytokines). Blood will be collected as follows: (1) 30ml in red-top tubes (no additive), and (2) 5ml in PaxGene RNA tubes, at 2.5ml blood apiece. 30ml of blood (red-top tubes) will be centrifuged and plasma will be stored in cryovials, and the PaxGene tubes will be stored as well; when it is time for assay, samples will be transferred to [name] laboratory. Standard freezer-proof labels will indicate participant ID and study session. Transport from the CRC to [name] laboratory will be managed by Clinical Research Center staff. Samples will be analyzed in small batches with all of one participant's samples being run in the same batch. Following assay, any additional serum will be stored by [name]. Following assay, the PaxGene RNA blood samples will be destroyed.

Clinical assessments and laboratory sampling for HC participants (Aim 3 substudy).

Point-of-care pregnancy test, urine toxicology screen, and laboratory samples via blood draw are identical for HC participants as described above.

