3 α -HSDII and 5 α -RI (the most expressed isoforms in the brain¹⁰⁵). The methodology to determine neuroactive steroid levels is a ‘state-of-the-art’ technique developed in co-PI [name]’s laboratory (GC-MS), which allows the simultaneous determination of neuroactive steroid from a single sample due to high sensitivity (fmolar) and unsurpassed structural specificity^{66,106–108}. Comparative qPCR determination of 5 α -RI and 3 α -HSDII expression⁶⁵ combined with complementary GC-MS measurement of neuroactive steroid has established a correlation among plasma and CSF neuroactive steroid biosynthesis in neurological disorders¹⁰⁹. Highly significant correlations were also established among CSF and post-mortem brain¹¹⁰ and CSF and serum neuroactive steroid levels^{66,111,68}. Importantly, Co-I [name]’s study of ALLO levels and 5 α -RI expression in human prefrontal cortex (BA9) is a further demonstration that down-regulation of neuroactive steroids in CSF⁶⁷ and blood¹¹² strongly reflects down-regulation of brain neuroactive steroid levels⁶⁵. Neuroactive steroid levels will be corrected for procedural losses by adding to the samples 1 pmol of deuterium-labeled neuroactive steroid used as internal standards^{107,108}. Measuring central mRNAs in peripheral tissues is easy to obtain, reliable, and known to closely reflect changes in neuroactive steroid biosynthesis occurring in the brain^{67,112}. The best source of mRNA is represented by isolated PBMC, since hemoglobin from erythrocytes can inhibit PCR¹¹³. Several neurological/psychiatric clinical studies have correlated brain with lymphocytes findings^{114,115}. Various groups confirmed the presence of 5 α -DHP and ALLO (GC-MS), 5 α -RI and 3 α -HSDII expression (PCR) in lymphocytes^{116,117}. The qPCR methodology is a suitable method to quantify mRNAs encoding for neurosteroidogenic enzymes expressed in PBMC and is a powerful tool in combination with GC/MS to determine alterations in neuroactive steroid biosynthesis (e.g., 3 α -HSDII and 5 α -RI, to evaluate altered regulation of ALLO biosynthesis). 3 α -HSDI and 5 α -RII (peripheral isoform) mRNA will also be measured and used as an internal control.

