In addition to the specific gene expression assays for neurosteroidogenic enzymes performed by [name], We will also perform “whole transcriptome shotgun sequencing” in each sample collected across both conditions, which measures the presence and quantity of RNA (related to the entire genome) in a given sample at a given moment. This will be used to test hypotheses regarding the effects of the manipulation on expression of genes coding for all neurosteroidogenic enzymes (not just those measured by [name] using qPCR), GABA-A receptor subunits, and inflammatory cytokines. These analyses will also be performed in-house at the University of Illinois.

Neuroactive steroids for HC participants (Aim 3 substudy).

Neuroactive steroids, mRNA, and genome sequence collection will be identical in the substudy as described above.

Smartphone-Based Assessments

Daily Symptoms Survey (3 minutes each evening throughout the 4-month Study). Each evening throughout the four months of the study, participants will complete the following self-report scales. First, the Daily Rating Form (DRF)⁵⁵, capturing hormone-related symptoms listed in the DSM-5^{118(p5)} (depression, hopelessness, worthlessness, anxiety, mood swings, rejection sensitivity, anger/irritability, interpersonal conflict, difficulty concentrating, lack of interest, insomnia, hypersomnia, overeating, lack of appetite, emotional overwhelm (hyperarousal), feeling out of control, fatigue, and physical discomfort). In addition to the DRF, participants will complete the Brief Agitation Measure (BAM)⁵⁴, a 3-item measure that taps into feelings of agitation (e.g., “I felt so stirred up inside that I wanted to scream”; hyperarousal) as well as dimensional ratings of the three highest-loading items from the Beck Hopelessness Scale¹⁷ (e.g., “The future seems dark to me”). This daily survey will provide an integrated rating of the patient’s symptoms across the entire day, consistent with methods used in seminal experiments of hormones and mood^{30,119,120}. Medication adherence, stressor exposure¹⁹, medication, drug, and alcohol use, sleep, pain, illness, and exercise will be recorded; any additional probing to clarify these online responses will be take place during the following day’s daily safety call.

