Testing Interactive Effects of Hopelessness and Arousal on Suicide Outcomes: Interactions among hopelessness and arousal will be examined as predictors of suicide outcomes and as mediators of the experimental effect. In order to test this, we examine day-to-day interactive effects of daily person-centered hopelessness (noted above) and daily person-centered arousal indices (noted above) predicting same-daily suicide outcomes (noted above). We predict that higher-than-usual hopelessness on a given day will predict greater same-day risk on suicide outcomes, but only when arousal is *also* higher than usual for that individual.

4. Evaluating Mediation Where Appropriate. Finally, each aim indicates that **mediation** will be explored as appropriate. Only when analyses indicate significant effects of the experiment on both the suicide outcome and any mediator, as well as significant associations between the person-centered variable (or interaction variable) and the suicide outcome, we will utilize methods provided by **Bauer, Preacher, and Gil (2006)** to construct a confidence interval for the level 1 indirect effect of experimental condition (condition X phase) on the suicide outcome via the mediator.

Testing for normative cyclical change in the HC group. Aim 3 seeks to characterize how gene expression for GABA_{AR} subunits varies across pre-specified menstrual cycle phase in response to hormonal change. In N=40 HC participants, we will run multilevel growth models to predict subunit gene expression (one model per gene) from specific cycle phase. We will test all pairwise comparisons between midluteal, perimenstrual, and midfollicular phases, controlling for ALLO level, to capture high P4 and ALLO states (midluteal), P4 and ALLO withdrawal (perimenstrual), and low P4 and ALLO (midfollicular).

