Testing for group differences between participants with past-month SI and HC. We hypothesize that clinical group moderates the effect of cycle phase on GABA_{AR} composition, such that the primary experimental group shows higher slope of midluteal-to-perimenstrual change in $\alpha 4$ and δ subunits, and lower $\gamma 2$ subunit replacement of δ subunit expression than the HC group. In one model of N=80 total participants, we will test the interaction of group and cycle phase on gene expression outcomes. We also hypothesize a correlation with symptoms, such that increases in $\alpha 4$ and δ subunit expression will be associated with increases in individuals with perimenstrual increases in SI. We also predict that even in the HC group, higher-than-average $\alpha 4$ or δ subunit expression will be associated with higher-than-average negative affect (e.g., depressed mood, anxiety, irritability, or perceived stress). We predict that higher $\gamma 2$ expression will be associated with lower negative affect and perceived stress. We will calculate a person-mean for each subunit's expression (mean level across 5 visits) and a deviation score at each visit (visit level minus person mean). We will test overall correlations (e.g., do participants with higher mean $\alpha 4$ expression have higher negative affect?) and interaction with cycle phase (e.g., does a perimenstrual increase in $\alpha 4$ expression *compared to person-mean* correlate with an increase in negative affect?). To further refine hypotheses, we will generate credible intervals using Bayesian methods in the context of multilevel modeling.

POWER ANALYSIS

80 completers achieves 80% power to detect conventionally small-to-medium sized effects that, in our estimation, are clinically meaningful (i.e., $f^2 = .10$, which would mean that the interaction of condition and phase had uniquely accounted for 10% of the variance in the outcome in the perimenstrual window; Selya et al., 2012, “*A Practical Guide to Calculating Cohen’s f^2 , a Measure of Local Effect Size*”). We posit that if hormone withdrawal (vs. experimental stabilization) does not account for at least 10% of the variance in the outcome during this critical risky window of the menstrual cycle, then this line of research, which involves significant participant burden, is not worth pursuing further.

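### Aim 3 reads blood RNA differences as GABA-A subunit gene regulation, but no model accounts for cell composition, so the two explanations cannot be separated

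*Protocol*

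**What the plan says.** **Specimen.** Protocol 6.0 (Clinical Laboratory Assessments and Sampling) draws "5ml in PaxGene RNA tubes, at 2.5ml blood apiece" at each laboratory visit. The stated targets of the RNA assays are "neurosteroidogenic enzymes, GABA-A receptor subunits, and other mechanisms such as inflammatory cytokines".

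**Sequencing.** Protocol 6.0 (Neuroactive Steroids) adds whole-transcriptome sequencing of each sample in both conditions, "which measures the presence and quantity of RNA (related to the entire genome) in a given sample at a given moment". It is to serve hypotheses on enzyme, GABA-A subunit and cytokine genes. The paragraph does not say which specimen is sequenced. For the healthy controls, "Neuroactive steroids, mRNA, and genome sequence collection will be identical in the substudy as described above".

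**Other cell sources named.** For the separate qPCR enzyme assay, the same section says "The best source of mRNA is represented by isolated PBMC". Protocol 2.0 instead refers to "neuroactive steroid biosynthetic enzyme mRNA expression in peripheral monocytes".

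**Interpretation.** Aim 3 in Protocol 3.0 is about plasticity of GABA-A receptor gene expression. Its hypotheses concern up-regulation of the α4 and δ genes, down-regulation of γ2, and a difference between groups in the change from midluteal to perimenstrual phase.

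**Models.** In the HC group (Protocol 10.0), "we will run multilevel growth models to predict subunit gene expression (one model per gene) from specific cycle phase", controlling for ALLO. For SI versus HC, in one model of 80 participants, "we will test the interaction of group and cycle phase on gene expression outcomes", with no covariate named. The laboratory-visit model for the experiment (Protocol 10.0; SAP, Analytic Steps) adjusts for pain, illness and as-needed medication.

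Neither document mentions a differential count, cell sorting before sequencing, or estimated cell fractions.

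**The concern.** A sample's RNA is the sum over the cells in it. If one cell type makes most of a transcript, the measured level moves whenever that cell type's share moves, even when every cell behaves as before. Regulation and composition then give the same number.

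Aim 3 makes the stronger of these two claims. It does not say only that blood levels of a transcript differ. It says that subunit genes are regulated across the cycle, and differently in people with suicidal ideation. The contrasts that carry this claim are between cycle phases, which are not assigned, and between SI and HC, which are not randomised. A significant phase or group-by-phase effect would leave an obvious rival explanation open, and nothing in the planned output would let a reader judge it.

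**Working it through.** **1. Nearest figure in the plan.** The documents give no figure for cell mix, so there is none to reproduce on the point itself. The closest is the SAP power row for PBMC gene expression: effective N 134, power .83. Its inputs are 85 completers, 4 − 0.25 = 3.75 visits, ICC .50, f² = .10, one-sided alpha .004 and 3 predictors.

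- N_eff = 85 × 3.75 / (1 + 2.75 × 0.50) = 318.75 / 2.375 = 134.2
- Noncentral t with df = 134 − 4 = 130 and noncentrality √(0.10 × 134) = 3.66 gives power 0.831

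Both reproduce. They are used in step 5 only to price the adjustment. Neither document gives a power calculation for Aim 3.

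**2. Which terms each model contains.**

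| Contrast | Covariates named | Cell-mix term |
|---|---|---|
| HC, phase | ALLO | none |
| SI vs HC, group by phase | none | none |
| Experiment, condition by phase (laboratory outcomes) | pain, illness, as-needed medication | none |

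**3. Size of the effect, assuming whole blood.** Let a cell class have share p, let it express the transcript r times as strongly as the other cells, and let its share rise by d with no change in any cell. Apparent expression is multiplied by

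1 + d(r − 1) / (1 + p(r − 1)),

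which becomes (p + d)/p when only that class makes the transcript. Take p = 0.35 (assumed):

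| Shift d | only that class | r = 10 | r = 5 | r = 2 |
|---|---|---|---|---|
| 0 points | 0% | 0% | 0% | 0% |
| 2 points | 0.37/0.35: 6% | 0.18/4.15: 4.3% | 0.08/2.40: 3.3% | 0.02/1.35: 1.5% |
| 5 points | 0.40/0.35: 14% | 0.45/4.15: 10.8% | 0.20/2.40: 8.3% | 0.05/1.35: 3.7% |
| 10 points | 0.45/0.35: 29% | 0.90/4.15: 21.7% | 0.40/2.40: 16.7% | 0.10/1.35: 7.4% |

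The share, the shift and the enrichment are all assumptions. If the class is mononuclear cells, the example does not carry over to isolated PBMC, where such cells are essentially the whole specimen. There the question would be the balance of lymphocytes and monocytes, for which no figure is available either.

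**4. What the design already controls.** Within-person phase comparisons cancel a person's stable cell mix, but not a shift that follows the cycle. In the group-by-phase term, a stable SI–HC difference largely cancels, but a difference in how the mix moves across phases does not. The planned correlations of person-mean expression with negative affect have no such protection. Criteria 8, 9 and 13 (autoimmune and other disease, nicotine and smoking, dysmenorrhea with immune signs) and visits at 7–11 am narrow the variation without measuring it. Illness is a covariate in the experimental laboratory model but is not named in either Aim 3 model.

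**5. What adjustment would cost.** Using the row in step 1, adding 1 to 5 fraction covariates unrelated to the contrast leaves power at 0.83. If they share a proportion R² of the contrast's variance, noncentrality becomes √(0.10 × (1 − R²) × 134):

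- R² = 10%: 3.47, power 0.78
- R² = 20%: 3.27, power 0.72
- R² = 30%: 3.06, power 0.64

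If three covariates instead explain 10% or 30% of residual variance without overlap, noncentrality is √(13.4/0.9) = 3.86 or √(13.4/0.7) = 4.38, and power is 0.88 or 0.95.

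**The case against.** The strongest reply is that the premise lies outside the documents. Nothing in them shows that leukocyte proportions shift with phase, condition or group, or that the subunit transcripts are cell-type specific. That stands, and it is why the point is conditional. A reader might infer that the trial will report composition shifts as gene regulation; the documents support only that the planned analysis could not tell the two apart.

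A reader might also infer that the randomised condition-by-phase contrasts are biased. They are not. Any change in cell mix caused by the hormones comes after treatment, so the unadjusted estimate is a valid total effect on blood expression. For the biomarker use raised in Protocol 2.0, that may be the quantity wanted.

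Nor can it be stated as fact that whole blood is sequenced. This is inferred from the collection tubes, and the documents name three cell sources. The point survives for PBMC, but the worked example may not.

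It is tempting to say that an effect which disappears on adjustment was composition all along. Step 5 shows why that fails: overlap alone can cut power from 0.83 to 0.64–0.78, and the adjustment conditions on a variable that hormones may affect.

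Finally, Protocol 2.0 labels the HC substudy exploratory, and none of the SAP's twelve outcomes is a sequencing outcome. That limits the weight of the point but does not answer it, because the plasticity conclusion is the stated purpose of Aim 3.

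**Conclusion.** The concern holds for Aim 3 as a limit on interpretation. As written, a phase or group-by-phase difference in subunit RNA cannot be attributed to gene regulation rather than to cell mix, and the exclusions, morning visits, illness covariate and within-person design reduce the ambiguity only in part.

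Its size is unknown. Under the whole-blood assumptions above, it runs from nothing at zero shift to 29% for a 10-point shift in the only cell class that makes the transcript, and to 7–22% for the same shift when enrichment is 2- to 10-fold. The absence of a cell-mix term and the non-randomised contrasts rest on the documents; the share, shift and enrichment do not.

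The randomised contrasts keep their meaning as total effects on blood expression. The two qPCR enzyme outcomes in the SAP also come from a cell mixture, but the same reasoning protects their condition-by-phase contrast. This is a cheap improvement to an exploratory aim, not a defect in the trial's primary analyses.

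**What to change.** - State which specimen is sequenced, and reconcile the references to PaxGene blood, PBMC and monocytes.
- Estimate leukocyte fractions for every sample from the planned sequencing data by marker-based deconvolution. Report the fractions themselves by phase and by group.
- Keep the unadjusted Aim 3 contrasts. Add a pre-specified sensitivity analysis with the fractions as visit-level covariates, and report both estimates with confidence intervals.
- Use the language of regulation or plasticity only where the adjusted estimate is consistent with the unadjusted one. Where it attenuates, say that composition and regulation cannot be separated, not that composition is proven.
- For the randomised condition-by-phase sequencing contrasts, keep the unadjusted estimate primary and treat the adjusted one as supportive only.

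**Cost.** No new samples, visits or staff are needed, only extra analysis of data already planned. The rule should be written before the expression data are analysed. The adjusted estimate is not the total effect, may be less precise (step 5), and assumes that the marker genes are not themselves hormone-responsive. Keeping both estimates in the report makes these limits visible.

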7.0 Expected Benefits/Risks

EXPECTED RISKS

1) Psychological Symptom Assessment. Clinical interviews and self-report assessments contain questions regarding sensitive personal information, including severe psychological symptoms such as suicidal and other impulsive behaviors (e.g., substance abuse). As a result, participants may become upset or embarrassed when discussing current or past distressing life events and behaviors. On the other hand, recent evidence suggests that research questions pertaining to potentially distressing topics such as psychiatric symptoms, suicidality, and sexual or physical abuse do not significantly increase distress or acute suicide risk in participants who report these issues^{124,125}. The chance of increased distress is necessary in order to assess how symptoms change in response to perimenstrual hormone withdrawal (vs. stabilization).

2) Effects of the Ovarian Hormone Stabilization Protocol on Mood/Anxiety and Behavior (for primary experimental group; N/A for HC group).

Mood/Anxiety. As the population being studied in this protocol will have elevated psychiatric symptoms, and as ovarian hormone changes are implicated in depression and anxiety symptoms in some females¹²⁶, it is possible that adverse mood reactions may occur (1) during the administration of ovarian hormones in the stabilization condition or (2) naturally during the placebo (natural) perimenstrual withdrawal condition. However, because the proposed hormone manipulation mimics (i.e., stabilizes) the luteal hormone levels that cycling individuals naturally experience⁹⁶, the proposed study is not expected to pose any greater risk to participants than what they experience in daily life. Furthermore, although the withdrawal from the experimental hormone condition could elicit negative mood changes, these are not expected to be any more severe than those that would otherwise have arisen from normal perimenstrual hormone withdrawal—that is, we will have simply delayed the normal withdrawal process. This argument is supported by the results of the prior K99 trial, where increases in symptoms observed during withdrawal from exogenous E2/P4 was less severe than that observed in the natural perimenstrual withdrawal condition under placebo.

Suicidality. As detailed above, the population will be recruited to achieve a population of individuals that is simultaneously: (1) experiencing recent suicidal ideation, yet (2) at acceptably low risk for suicidal crisis/attempt (such that the participant is appropriate for outpatient rather than inpatient care) based on an assessment conducted during the enrollment visit. Because ovarian hormone changes are implicated in psychiatric symptoms in some females, and because such symptoms may increase suicide risk, it is possible that increases in suicidality may occur (1) during the administration of ovarian hormones in stabilization conditions or (2) naturally during the placebo (natural) perimenstrual withdrawal condition. However, because the proposed hormone manipulation mimics (i.e., stabilizes, then shifts) the normal physiologic range of luteal hormone levels and changes that cycling individuals naturally experience, the proposed study is not expected to expose participants to greater risk for suicidality than what they experience in daily life. As above, this argument was supported in the prior K99 trial, where increases in proximal suicide risk observed during withdrawal from exogenous E2/P4 was less severe than that observed in the natural perimenstrual withdrawal condition under placebo.

3) Hormone Side Effects (for primary experimental group; N/A for HC group). We do not expect any adverse side effects associated with the hormonal manipulations outlined in this protocol following reasons: First, we did not observe any side effects occurring significantly more frequently under active hormones than during placebo during the prior K99 trial using the same hormonal manipulation. Second, we will be administering the physiologically relevant steroid hormones (estradiol and/or progesterone) and not the substituted steroids (such as ethinyl estradiol or norethindrone) present in many oral contraceptives, the latter of which have been reported to have potentially more serious side effects¹²⁷⁻¹²⁹. Nevertheless, we describe the common side effects of estradiol and progesterone below.

Estradiol. Nausea is the most common side effect of estrogen administration. At conventional hormone doses, this complaint seldom interferes with eating, and no weight loss has been reported as a result of nausea. Breast engorgement and bleeding are also common side effects of estrogen administration. Pre-existing fibroid tumors of the uterus may enlarge under the effects of estrogen; however, at the dosage and for the duration of estrogen administration in this protocol this risk is extremely small. Numerous retrospective case control studies published since 1975 have indicated that postmenopausal exposure to unopposed estrogens for more than one year results in a two to 12-fold increased relative risk for endometrial cancer. A relationship between the dose and duration of estrogen use and the risk for endometrial cancer has also been shown, the risk being increased after one to four years of estrogen use and rising also with the dosage employed. However, the addition of progesterone to estrogen replacement therapy decreases the risk of endometrial hyperplasia and endometrial cancer to equal or below that of females receiving no hormonal treatment, and oral prometrium of 200 mg/day, as is present in the proposed work, is sufficient to prevent endometrial hyperplasia¹³⁰. There is an increase in thromboembolism in females receiving non-contraceptive estrogen therapy¹³¹⁻¹³³, but this risk is most evident in obese females and in those who smoke (exclusionary factors in the present research).

It may be important to note that there were numerous concerns about increased risk for breast cancer and cardiovascular events related to the use of hormone replacement therapy (estrogen plus a progestin) that stemmed from the initial results of the Women's Health Initiative (WHI), which randomized 27,000 postmenopausal females to HRT or placebo. Critical

reviews subsequent to the initial WHI reports showing an increased incidence of non-fatal breast cancer and cardiovascular events have argued that the discordant findings between the WHI and the observational studies finding benefit of HRT for all cause and cardiovascular mortality reflected problems in the design of the WHI, the most important of which may have been the age and condition of the study subjects¹³⁴. As the risk of breast cancer, heart disease and metabolic dysregulation increase with age; the likelihood of adverse events upon exposure to E2 should also increase with age. Recent reports from the North American Menopause Society¹³⁵ and the Endocrine Society¹³⁶ confirm that the risk of CVD in the WHI was observed in older but not younger females. Additionally, data suggest that the formulation of E2 (conjugated equine estrogen) used in the WHI is associated with an increased profile of risk compared with transdermal E2, and the progestin used in the WHI (medroxy progesterone acetate) is particularly antagonistic (among progestins) to the beneficial cardiovascular effects of E2¹³⁷.

Given our plans to administer transdermal E2 to females: (1) for only 14 days, (2) no older than 45 years of age, (3) who are currently regularly menstruating and medically healthy, and (4) who are at no greater than average risk for CVD, breast cancer or VTE, **the risk of serious adverse events is exceedingly low**.

Progesterone. Progesterone and the synthetic progestins are widely prescribed, with indications including dysfunctional uterine bleeding, endometriosis, mastodynia, galactorrhea, and precocious puberty¹³⁰. In a recent study, a dose of 300 mg of oral micronized progesterone was given to a sample of females with premenstrual mood disturbance and was well tolerated by this sample¹³⁸. Side effects reported included lightheadedness and fatigue; these were very mild and caused no dropouts.

4) Confidentiality. A breach of confidentiality could indicate to others a participants' history of mental and behavioral health concerns.

5) Venipuncture. Venipuncture (the needle stick during blood draws) may result in syncope (lightheadedness), discomfort, nausea, and bruising. There is a very low risk of infection from venipuncture (less than 1 in 1000).

6) Oura Ring. The small flashing light on the oura ring could theoretically increase risk of seizure among those with epilepsy (exclusionary in the present study), and could theoretically interfere with pacemakers and other internal electronic devices (also exclusionary in the present study).

PROTECTION AGAINST RISKS

Protections Against Risks Associated with Psychological Assessment. The PI ([name]) is a licensed clinical psychologist with ten years of experience in risk assessment and empirically-supported treatment of chronic suicidality (e.g., Dialectical Behavior Therapy). The PI has personally conducted roughly ten studies assessing daily emotional symptoms, three of which included measures of daily suicidal ideation and depressive symptoms in females with borderline personality disorder or chronic suicidality. Based on these experiences and the available literature, participants are unlikely to become acutely upset in response to the psychological assessments conducted in the present study. If participants do become upset during an assessment, they will be reminded of their right to discontinue participation, suicidal ideation will be assessed and managed using the University of Washington Risk Assessment and Management Procedure (UWRAP) as recommended by NIMH, and appropriate referrals will be made. Participants will be reminded each day that they do not have to answer any question that they do not want to answer.

1) Protections Against Risks Associated with E2 and P4 Administration (*for primary experimental group; N/A for HC group*). Hormone-related risks are minimized in our protocol by the following: 1) including only young, medically healthy premenopausal females; 2) the use of a very short-term administration of estradiol in combination with oral micronized progesterone will virtually prevent the chance of endometrial hyperplasia; 3) exposure to E2 for less than 3-5 years has not been shown to be associated with an increased risk of breast cancer^{133,139}; 4) the exclusion of individuals with a family

history indicative of increased breast cancer risk or thromboembolic disorders; 5) the frequent assessment of side effects at every phone call; 6) provision of a drug information sheet with the instruction to call the study doctors immediately if any of the following symptoms are experienced: abnormal or prolonged vaginal bleeding, severe headaches, changes in vision or speech, dizziness or faintness, pains in calves or chest, or sudden shortness of breath; 7) banking a prescription for a back-up, additional 3 pills with the investigational drug service for each participant in an active condition will prevent participants from missing study medication doses on days they are in the lab should they forget to bring their study medication with them to the lab visit; 8) the development of a safety monitoring plan (see below); and 9) monitoring for adverse events by a Data and Safety Monitoring Committee.

2) Effects of the Ovarian Hormone Stabilization Protocol on Mood and Suicidality (for primary experimental group; N/A for HC group).

The following measures will be taken to mitigate any negative impact of the experiment on mood or suicidality:

Depressive symptoms and suicidality will be monitored during a daily evening telephone call during each condition and will also be measured and monitored via smartphone surveys. These daily calls will be carried out by trained research assistants, and the PI will be on-call during these calls. In the case of **(A) severe mood changes** (defined below) or **(B) imminent risk for suicide attempt (requiring inpatient hospitalization)**, participation will be discontinued and the individual will be referred for an appropriate level of psychiatric care. Protocols for assessing severity of mood symptom changes, evaluating suicide risk, and discontinuation and referral are described below.

Protocol for Assessing Emergence of Severe Mood Changes. Because they will be recruited for recent suicidality, participants are expected to show elevated baseline levels of mood symptoms. Therefore, the emergence of severe mood symptoms will be defined as three days of daily depression scores (defined as depression, hopelessness, and worthlessness/guilt on the daily symptom record as defined in the research strategy) that are 1) severe or extreme in nature (i.e., above “moderate” on the response scale), 2) at least 50% increased over their self-reported trait levels of depression (as defined by mean scores on these items across the baseline month), 3) maintained for three consecutive days, and 4) a clinical interview must reveal that this worsening of mood is significantly impacting functioning in relationships or ability to engage with work or school. Should such an acute, impairment-related worsening of depression persist for three days, the **Protocol for Discontinuation and Referral** described below will be followed to remove the participant from the study and ensure proper engagement with their mental health provider at the appropriate level of psychiatric care.

Protocol for Assessing the Emergence of Imminent Risk of Suicide Attempt. Participants will be recruited to be at acceptably low current risk for suicide attempt given historical factors as described above. Daily telephone assessments will end with a structured screening for current suicide risk, including suicidal ideation, planning, and intent using the University of Washington Risk Assessment and Management Protocol (or UWRAP; also known as the Linehan Risk Assessment Procedure or LRAP)¹²⁵. The UWRAP is the suicide risk assessment and protocol recommended by the NIMH for use in RCTs when participants are not in an ongoing treatment relationship with the assessor. **The purpose of this daily UWRAP screening is to determine (1) whether the participant’s current risk of a suicide attempt has elevated to imminent risk for suicide attempt according to established guidelines¹²⁵ and to (2) intervene as appropriate to reduce any emergent imminent suicide risk.** The UWRAP allows the screener to determine the participant’s current risk status for a suicide attempt, and provides concrete, structured guidelines for appropriate actions at each level of risk specifically in the context of a research study. UWRAP protocols will be followed closely. The UWRAP also includes a template for documenting specific risk classifications based on the participant’s responses and the screener’s actions. A UWRAP note will be written for each daily contact where nonzero suicidality is reported; notes in which any suicidal ideation is reported will be immediately reviewed with the PI, and will be discussed at weekly and monthly team meetings. Should an individual’s responses to the UWRAP indicate imminent current risk for suicide attempt according to established standards, the **Protocol for Discontinuation and Referral** described below will be followed to remove the participant from the study and to ensure the appropriate level of psychiatric care.

